## CLINICAL TRIAL PROTOCOL SYNOPSIS

Company name	Boehringer Ingelheim
Protocol date	19 March 2019
Revision date	19 July 2019
BI trial number	1346-0039
Title of trial	A study to investigate the effects of memantine on the pharmacokinetics of BI 425809 and vice versa in healthy male and female subjects (non-randomized, single-arm, open-label, three-period, one fixed sequence cross-over study)
Principal Investigator:	
Trial site	
Clinical phase	I
Trial rationale	Memantine is a common medication used in patients diagnosed with Alzheimer's Disease (AD). Since BI 425809 is developed as a symptomatic treatment for AD it is very likely that it may be used on top of memantine in clinical practice. Therefore, it is crucial to investigate if there are any relevant pharmacokinetic interactions between BI 425809 and memantine when administered together before their concomitant use could be allowed in Phase 3 trials and later in clinical practice.
Trial objectives	To investigate the effect of steady state exposure of memantine on the steady-state pharmacokinetics of BI 425809 and vice versa in healthy subjects
Trial design	Non-randomized, single arm, open-label, three-period, one fixed sequence cross-over design
Trial endpoints:	Primary endpoints: 

• <math>AUC_{\tau,ss}</math> and <math>C_{max,ss}</math> of BI 425809 in blood

• <math>AUC_{\tau,ss}</math> and <math>C_{max,ss}</math> of memantine in blood

Number of subjects total entered	N = 16
Diagnosis	Not applicable
Main criteria for inclusion	Healthy male/female subjects, age of 18 to 50 years (inclusive), body mass index (BMI) of 18.5 to 29.9 kg/m  (inclusive)
Trial product 1 dose mode of admin.	BI 425809, film coated tablet 25 mg Oral with 240 mL of water after an overnight fast of at least 10 h
Trial product 2 dose mode of admin.	Memantine film-coated tablets 5 mg, 10 mg, 15 mg, 20 mg Oral administration with 240 mL of water. Memantine dosing follows an up-titration regime from 5 mg to 20 mg for tolerability reasons

Proprietary confidential information © 2019 Boehringer Ingelheim International GmbH or one or more of its affiliated companies

Duration of treatment	
Period 1 = Visit 2: Treatment R1 (Reference 1 = BI 425809 alone)
 
Trial product 1: Days 1-10: multiple doses of 25 mg BI 425809 q.d.
 
Period 1 and 2 will be separated by a wash-out phase of at least 7 days between last treatment administration in Period 1 and first treatment administration in Period 2.
 
Period 2 = Visit 3: Up-Titration to R2 followed by Treatment R2 (Reference 2 = Memantine alone)
 
Trial product 2: Up-titration regimen to Treatment R2, i.e.
 
Days 1-7: multiple doses of 5 mg memantine q.d.
 
Days 8-14: multiple doses of 10 mg memantine q.d.
 
Days 15-21: multiple doses of 15 mg memantine q.d.
 
Days 22-28: multiple doses of 20 mg memantine q.d.
 
Trial product 2: Treatment R2, i.e.
 
Days 29-35: multiple doses of 20 mg memantine q.d
 
Period 3 = Visit 4: Treatment T (Test = BI 425809 + Memantine)
 
Trial product 1: Days 1-10 multiple doses of 25 mg BI 425809 q.d.
 
Trial product 2: Days 1-10 multiple doses of 20 mg memantine q.d.
 
Period 3 follow directly of period 2, i.e. the last day of period 2, is the calendar day before the first day of period 3.

Statistical methods	
The effects of BI 425809 on the pharmacokinetics of memantine (T to R1) and the effects of memantine on the pharmacokinetics of BI 425809 (T to R2) will be evaluated based on the ratio (test to reference treatment) of the point estimates of the geometric means (gMeans) for the primary and secondary PK endpoints. Additionally, their two-sided 90% confidence intervals (CIs) will be provided. This method corresponds to the two one-sided t-test procedure, each at a 5% significance level. Since the main focus is on estimation and not testing, a formal hypothesis test and associated acceptance range is not specified. The statistical model will be an analysis of variance (ANOVA) on the logarithmic scale including effects for 'subject' and 'treatment'. CIs will be calculated based on the residual error from the ANOVA.
 
Descriptive statistics will be calculated for all endpoints.

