## 7. STATISTICAL METHODS AND DETERMINATION OF SAMPLE SIZE

### 7.1 STATISTICAL DESIGN – MODEL

The main objectives of this trial are to investigate the relative bioavailability of

- 25 mg of BI 425809 in Steady State when given alone (Reference 1, R1) compared with co-administration of 25 mg of BI 425809 and 20 mg of memantine both in Steady State (Test, T),

and the relative bioavailability of

- 20 mg of memantine in Steady State when given alone (Reference 2, R2) compared with co-administration of 25 mg of BI 425809 and 20 mg of memantine both in Steady State (Test, T),

following oral administration on the basis of the primary pharmacokinetic endpoints, as listed in [Section 2.1.2](#) and [2.1.3](#). The trial is designed to allow intra-subject comparisons and will be evaluated statistically by use of a linear model for logarithmically transformed PK endpoints.

A further objective is to evaluate and compare further pharmacokinetic parameters between the treatments. These pharmacokinetic parameters will be assessed by descriptive statistics.

The assessment of safety and tolerability is a further objective of this trial, and will be evaluated by descriptive statistics for the parameters specified in [Section 2.2.2.2](#).

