7.4 PRIMARY ENDPOINTS

7.4.1 Primary analysis of the primary endpoints

Primary analysis of the primary endpoints will be performed as defined in Sections 7.3.1 of the CTP.

The statistical model for the primary analysis defined in the CTP is an analysis of variance (ANOVA) model on the logarithmic scale including "treatment" as fixed effects and "subject" as random effect. Relative bioavailability of the study treatments will be estimated by the ratios of the geometric means of (T/R1) and (T/R2) of the primary endpoints.

Exclusion of PK parameters

The ADS ADPP contains column variables APEXC and APEXCO indicating inclusion/exclusion (APEXC) of a PK parameter and an analysis flag comment (APEXCO). All analyses based on the PKS are based on PK parameter values which are not flagged for exclusion, i.e. with APEXC equal to "Included".

Exclusion of plasma concentrations

The ADS ADPC (PK concentrations per time-point or per time-interval) contains column variables ACEXC or ACEXCO indicating inclusion/exclusion (ACEXC) of a concentration and an analysis flag comment (ACEXCO). Exclusion of a concentration depends on the analysis flag comment ACEXCO. For example, if ACEXCO is set to "ALL CALC", the value will be excluded for all types of analyses based on concentrations. If ACEXCO is set to "DESC STATS" the value will be excluded from descriptive evaluations per planned time

point/time interval. If ACEXCO contains the addition "TIME VIOLATION" or "TIME DEVIATION", the value can be used for further analyses based on actual times. If ACEXCO is set to "HALF LIFE", the value will be excluded from half-life calculation only; the value is included for all other analyses. Excluded concentration itself will be listed in the CTR associated with an appropriate flag.

Further details are given in "Noncompartmental Pharmacokinetic / Pharmacodynamic Analyses of Clinical Studies" (4) and "Description of Analytical Transfer Files and PK/PD Data Files" (5).

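### Does the synopsis's swap of the two reference treatments leave the primary comparisons undefined?

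*Protocol*

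**What the plan says.** The synopsis defines the three treatments under duration of treatment: "Treatment R1 (Reference 1 = BI 425809 alone", "Treatment R2 (Reference 2 = Memantine alone" and "Treatment T (Test = BI 425809 + Memantine" (closing brackets omitted here and below). Protocol Table 4.1.4: 1 gives the same R1, R2 and T.

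The statistical methods row of the synopsis then pairs the drugs with the references the other way round. For memantine exposure it gives "The effects of BI 425809 on the pharmacokinetics of memantine (T to R1"; for BI 425809 exposure it gives "the effects of memantine on the pharmacokinetics of BI 425809 (T to R2". It also says the ratios will be given for secondary PK endpoints. Protocol Sections 2.1.3 and 7.3.2 and SAP Sections 5.2.2 and 7.5.2 say there are none.

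Protocol Section 7.1 has the comparisons as "25 mg of BI 425809 in Steady State when given alone (Reference 1, R1) compared with co-administration" and "20 mg of memantine in Steady State when given alone (Reference 2, R2) compared with co-administration". Section 7.2 compares each drug alone with the same drug co-administered. Section 7.3.1 gives the model with a generic test and reference and two treatment levels per endpoint.

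SAP Section 7.4.1 says: "Relative bioavailability of the study treatments will be estimated by the ratios of the geometric means of (T/R1) and (T/R2) of the primary endpoints". It names no analyte, but it runs the primary analysis as defined in protocol Section 7.3.1. SAP Section 3 states that the SAP is based on the analysis specification in protocol Section 7.

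**The concern.** These are the trial's only two primary comparisons, and the synopsis has both the wrong way round. The effect of BI 425809 on memantine needs memantine given alone as its reference, which is R2. The effect of memantine on BI 425809 needs R1. As the synopsis words them, neither ratio has a usable denominator.

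The SAP sentence does not settle the matter by itself. Read literally, it crosses two ratios with four endpoints, and half of those combinations do not exist. A reader who took the synopsis as the key to tables headed T/R1 and T/R2 could attribute each interaction to the wrong drug. The purpose of the trial is to say which drug, if either, alters exposure to the other, so such an error would matter.

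**Working it through.** **1. The plan's own figures.** Table 7.7: 1 states precision (upper confidence limit divided by the estimate) reached with 95% probability. For paired data:

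- σ = √ln(1 + gCV²)
- ω = t(0.95, n−1) × σ × √(2/n) × √[χ²(0.95, n−1)/(n−1)]
- precision = exp(ω), with limits 100 × exp(±ω)

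Inputs from protocol Section 7.7: n = 16, and gCV 24% (BI 425809 AUC) or 7.7% (memantine). With 15 degrees of freedom, t = 1.753 and χ² = 24.996, so the last factor is √(24.996/15) = 1.291. Also √(2/16) = 0.3536.

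- BI 425809: σ = √ln(1.0576) = 0.2366. ω = 1.753 × 0.2366 × 0.3536 × 1.291 = 0.189. Precision 1.2085, limits 82.75 to 120.85.
- Memantine: σ = √ln(1.005929) = 0.0769. ω = 1.753 × 0.0769 × 0.3536 × 1.291 = 0.0615. Precision 1.0634, limits 94.03 to 106.34.

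Both agree with the table, as do its other 14 rows. The table is organised by drug and uses neither R1 nor R2, so the labels do not enter the sample size argument.

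**2. The pairings side by side.**

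| Place | Reference for BI 425809 | Reference for memantine |
|---|---|---|
| Synopsis, statistical methods | R2 | R1 |
| Protocol Section 7.1 | R1 | R2 |
| Protocol Section 7.2 | BI 425809 alone | memantine alone |
| Protocol Section 7.3.1 | not named | not named |
| SAP Section 7.4.1 | not named | not named |

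Only the synopsis row conflicts with the treatment definitions. The definitions used here are those of the synopsis and protocol Table 4.1.4: 1. The row labels of SAP Table 6.1: 1 look displaced in the text copy, so that table is not relied on.

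**3. Could the synopsis pairing produce a number?**

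- Memantine, T to R1: memantine is first dosed in Period 2, after R1 has ended. R1 contains no memantine exposure.
- BI 425809, T to R2: the wash-out is at least 7 days from the last Period 1 dose to the first Period 2 dose. The R2 profile is on Day 35, 34 days after that first dose. The interval is at least (7 + 34) × 24 = 984 h. The half-life is 37 to 59 h (protocol Section 1.2.1.4), so 984/59 = 16.7 to 984/37 = 26.6 half-lives have passed. The remaining fraction is 2^−16.7 ≈ 9.5 × 10⁻⁶ down to 2^−26.6 ≈ 9.9 × 10⁻⁹. The Flow Chart row for the Day 35 dose also marks a memantine sample and no BI 425809 sample.

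Under the Section 7.3.1 model each endpoint has two treatment levels. With the synopsis pairing one level would have no usable data, and the treatment effect could not be estimated. With the Section 7.1 pairing both levels have a planned steady-state profile.

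**The case for a change.** The best case for acting is that this is current text, not amendment history, and that it covers every primary comparison. The SAP is supposed to give detailed procedures, yet it sends the reader to protocol Section 7.3.1, which is equally generic. The pairing emerges only on going back to Section 7.1. SAP Section 4 declares agreement with the protocol without noticing that the protocol disagrees with itself. Two lines of text would remove the doubt, and the result is meant to inform combined use in Phase 3, where direction matters.

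The facts in this stand: the labels are swapped, the SAP does not name the analyte for each ratio, and the mention of secondary PK endpoints is left-over wording.

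The harm does not follow. If the contrasts are undefined as the synopsis words them, following it gives an empty table that is noticed at once. A plausible but misattributed result would require someone to compute the right ratio under Section 7.1 and then label it from the synopsis, against the treatment definitions. Even then, each primary endpoint is a parameter of a named analyte. A ratio for memantine AUC shows the effect on memantine whichever reference code stands in the heading. The secondary wording has no analysis attached to it.

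**Conclusion.** The slip is real but clerical, and it is confined to one sentence of the synopsis. Two reference codes are exchanged. The governing statistical section gives the right pairing, the SAP takes its specification from that section, and the design allows no other pairing. The SAP's silence on analyte is a gap that any analyst fills correctly, because each ratio can be computed for only one drug.

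The effect on the results is nil. The four ratios, their 90% intervals, the model and the planned precision (1.208 and 1.063 at 16 subjects) are the same whether or not the synopsis is tidied.

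This rests on the analysts working from protocol Section 7, as the SAP says they do, and on the treatment definitions, which agree between the synopsis and protocol Table 4.1.4: 1. The residue figure further assumes simple exponential decline at the stated half-lives and the minimum wash-out. A longer wash-out would only make it smaller. No change to the plan is called for.

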## FLOW CHART

Period	Visit	Day	Planned time (relative to first drug administration) [h:min]	Approximate clock time of actual day [h:min]	Event and comment	Safety laboratory	Safety assessments	PK BI 425809 blood	PK memantine blood	PK urine memantine	C-SSRS	Vital signs (BP, PR) & 12-lead ECG	Questioning for AEs and concomitant therapy 
SCR	1	-21 to -1			Screening (SCR) 	x	x 				x	x	
1 	2	2	-1	-14:00	18:00	Admission to trial site	x 	x 			x		x
		1	1	-2:00	06:00	Allocation to subject numbers 	x 		x 	x 		x 	x 
				0:00	08:00	Administration of 25 mg BI 425809							
				0:30	08:30				x				
				1:00	9:00				x				
				2:00	10:00	240 mL fluid intake			x				
				3:00	11:00				x				
				3:30	11:30				x				
				4:00	12:00	240 mL fluid intake, thereafter lunch 			x			x	x
				4:30	12:30				x				
				5:00	13:00				x				
				6:00	14:00				x				
				7:00	15:00				x				
				8:00	16:00	Snack (voluntary)			x				
				10:00	18:00				x				
				11:00	19:00	Dinner 						x	x
				12:00	20:00				x				
		2	24:00	08:00	Administration of 25 mg BI 425809	x		x 					x
			25:00	09:00	Breakfast (voluntary), discharge from trial site						x	x	
		3	48:00	08:00	Ambulatory visit, Administration of 25 mg BI 425809							x	
		4	72:00	08:00	Ambulatory visit, Administration of 25 mg BI 425809							x	
		5	96:00	08:00	Ambulatory visit, Administration of 25 mg BI 425809	x						x	
		6	120:00	08:00	Ambulatory visit, Administration of 25 mg BI 425809							x	
		7	144:00	08:00	Ambulatory visit, Administration of 25 mg BI 425809							x	
		8	168:00	08:00	Ambulatory visit, Administration of 25 mg BI 425809							x	

Proprietary confidential information © 2019 Boehringer Ingelheim International GmbH or one or more of its affiliated companies

Period	Visit	Day	Planned time (relative to first drug administration) [h:min]	Approximate clock time of actual day [h:min]	Event and comment	Safety laboratory	Safety assessments	PK_BI 425809 blood	PK_memantine blood	PK_urine memantine	C-SSRS	Vital signs (BP, PR) & 12-lead ECG	Questioning for AEs and concomitant therapy 
2 	3 	9	192:00	08:00	Ambulatory visit, Administration of 25 mg BI 425809	x					x		x
			202:00	18:00	Admission to trial site	x 	x 			x		x	
		10	216:00	08:00	Administration of 25 mg BI 425809		x 				x 	x 	
			216:30	08:30			x						
			217:00	09:00			x					x	
			218:00	10:00	240 mL fluid intake		x					x	
			219:00	11:00			x					x	
			219:30	11:30			x						
			220:00	12:00	240 mL fluid intake, thereafter lunch 		x				x	x	
			220:30	12:30			x						
			221:00	13:00			x						
			222:00	14:00			x					x	
			223:00	15:00			x						
			224:00	16:00	Snack (voluntary) 		x					x	
			226:00	18:00			x					x	
			227:00	19:00	Dinner								
			228:00	20:00			x				x	x	x
		11	240:00	08:00	Breakfast (voluntary)  , discharge from trial site	x	x 	x			x	x	x
			-2:00	06:00	Admission to trial site	x 	x 		x 	x	x 	x 	x 
			0:00	08:00	Administration of 5 mg Memantine					— 			
			0:30	08:30			x						
			1:00	09:00			x					x	
			2:00	10:00	240 mL fluid intake		x					x	
			3:00	11:00			x					x	
			3:30	11:30			x						
			4:00	12:00	240 mL fluid intake, thereafter lunch 		x	—		x		x	
			4:30	12:30			x						
			5:00	13:00			x						
			6:00	14:00			x					x	
			7:00	15:00			x						
			8:00	16:00	Snack (voluntary) 		x	—		x		x	
			10:00	18:00			x					x	
			11:00	19:00	Dinner								
			12:00	20:00			x	—		x		x	
		2	24:00	08:00	Administration of 5 mg Memantine			x 	—	x 	x 	x 	
			25:00	09:00	Breakfast (voluntary)  , discharge from trial site		x 			x	x	x	
		3 - 7	48:00 	08:00	Ambulatory visit, Administration of 5 mg Memantine	x 					x 	x 	

Proprietary confidential information © 2019 Boehringer Ingelheim International GmbH or one or more of its affiliated companies

Period	Visit	Day	Planned time (relative to first drug administration) [h:min]	Approximate clock time of actual day [h:min]	Event and comment	Safety laboratory	Safety assessments	PK BI 425809 blood	PK memantine blood	PK urine memantine	C-SSRS	Vital signs (BP, PR) & 12-lead ECG	Questioning for AEs and concomitant therapy 
3	4 	8 -14	168:00 	08:00	Ambulatory visit, Administration of 10 mg Memantine	x 	x 		x 			x 	x 
			336:00 	08:00	Ambulatory visit, Administration of 15 mg Memantine	x 	x 		x 			x 	x 
			504:00 	08:00	Ambulatory visit, Administration of 20 mg Memantine	x 	x 		x 			x 	x 
			792:00	08:00	Ambulatory visit, Administration of 20 mg Memantine				x 			x	x
			802:00	18:00	Admission to trial site	x 	x 				x		x
		35	816:00	08:00	Administration of 20 mg Memantine	x 			x 	— 		x 	x 
			816:30	08:30					x				
			817:00	09:00					x				x
			818:00	10:00	240 mL fluid intake				x				x
			819:00	11:00					x				x
			819:30	11:30					x				x
			820:00	12:00	240 mL fluid intake, thereafter lunch 				x	—			x
			820:30	12:30					x				
			821:00	13:00					x				
			822:00	14:00					x				x
			823:00	15:00					x				
			824:00	16:00	Snack (voluntary) 				x	—			x
			826:00	18:00					x				x
			827:00	19:00	Dinner							x	x
			828:00	20:00					x	—		x	x
		1	0:00	08:00	Administration of 25 mg BI 425809 and 20 mg Memantine	x		x 	x 	—		x 	x 
			1:00	09:00	Snack (voluntary) 								
			2:00	10:00									
			4:00	12:00	lunch 							x	x
			6:00	14:00									
			8:00	16:00	Snack (voluntary) 							x	x
			10:00	18:00									
			11:00	19:00	Dinner							x	
		2	24:00	08:00	Administration of 25 mg BI 425809 and 20 mg Memantine							x 	x
			48:00	08:00	Administration of 25 mg BI 425809 and 20 mg Memantine							x 	x 
			49:00	09:00	Breakfast (voluntary)  , discharge from trial site		x 				x	x	x

Proprietary confidential information © 2019 Boehringer Ingelheim International GmbH or one or more of its affiliated companies

Period	Visit	Day	Planned time (relative to first drug administration) [h:min]	Approximate clock time of actual day [h:min]	Event and comment	Safety laboratory	Safety assessments	PK B 425809 blood	PK m emantine blood	PK w urine memantine	C-SSRS	Vital signs (BP, PR) & 12-lead ECG	Questioning for AEs and concomitant therapy 
		4	72:00	08:00	Ambulatory Visit: Administration of 25 mg BI 425809 and 20 mg Memantine	x					x 	x 	
		5	96:00	08:00	Ambulatory Visit: Administration of 25 mg BI 425809 and 20 mg Memantine			x 	x 		x 	x 	
		6	120:00	08:00	Ambulatory Visit: Administration of 25 mg BI 425809 and 20 mg Memantine			x 	x 		x 	x 	
		7	144:00	08:00	Ambulatory Visit: Administration of 25 mg BI 425809 and 20 mg Memantine							x 	
		8	168:00	08:00	Ambulatory Visit: Administration of 25 mg BI 425809 and 20 mg Memantine							x 	
		9	192:00	08:00	Ambulatory Visit: Administration of 25 mg BI 425809 and 20 mg Memantine			x 	x 		x 	x 	
		10	202:00	18:00	Admission to trial site	x 	x 				x		x
			216:00	08:00	Administration of 25 mg BI 425809 and 20 mg Memantine	x 		x 	x 	— 		x 	x 
			216:30	08:30				x	x				
			217:00	09:00				x	x			x	
			218:00	10:00	240 mL fluid intake			x	x			x	
			219:00	11:00				x	x			x	
			219:30	11:30				x	x			x	
			220:00	12:00	240 mL fluid intake, thereafter lunch 			x	x	—		x	
			220:30	12:30				x	x			x	
			221:00	13:00				x	x			x	
			222:00	14:00				x	x			x	
			223:00	15:00				x	x			x	
			224:00	16:00	Snack (voluntary) 			x	x	—		x	
			226:00	18:00				x	x			x	
			227:00	19:00	Dinner								
			228:00	20:00				x	x	—		x	
		11	240:00	08:00	Breakfast (voluntary)  , discharge from trial site	x 	x	x	—		x	x	x
		18			Phone call								x
FU	5	32-37			End of trial (EoTrial) examination 	x	x 				x	x	x

Proprietary confidential information © 2019 Boehringer Ingelheim International GmbH or one or more of its affiliated companies

1. Subject must be informed and written informed consent obtained prior to starting any screening procedures. Screening procedures include physical examination, check of vital signs, visual tests, C-SSRS assessment, ECG, safety laboratory (including drug screening and alcohol breath test), demographics (including determination of body height and weight, smoking status and alcohol history), relevant medical history, concomitant therapy and review of inclusion/exclusion criteria
2. The time is approximate; the procedure is to be performed and completed within the 2 h prior to drug administration.
3. If several actions are indicated at the same time, the intake of meals will be the last action.
4. End of trial examination includes physical examination including neurological assessment, vital signs, visual tests, C-SSRS assessment, ECG, safety laboratory, recording of AEs and concomitant therapies.
5. Only urine drug screening and alcohol breath test as well as pregnancy test in women will be done at this time
6. AEs and concomitant therapies will be recorded throughout the trial, but will be specifically asked for at the times indicated in the [Flow Chart](#) above.
7. There will be no further wash-out period between visit 3 and 4, i.e. Day 1 of Visit 4 the following calendar day of Day 35 visit 3
8. The sample is to be taken within 10 min prior to next dosing
9. During the up-titration phase to steady state vital signs, ECG and AE/CT questioning is performed on each day prior to memantine medication
10. During the up-titration phase to steady state safety lab is taken at the last day of each memantine dose level
11. Only on day 22 and 33
12. Neurological assessment for details refer to [Section 5.2.1](#)
13. A blank urine sample (x) is to be obtained prior to administration of trial medication. Other urine samples are to be collected over the stated post-dose intervals as indicated above. For technical reasons the planned stop time of the urine sample obtained starting visit 3, 828:00, will be 840:00.
14. Only on day 28
15. The column “planned time” only includes start time of the first day of the respective interval of days
16. To be done on the first day of each dose level
17. Visual tests, for details refer to [Section 5.2.3](#)
18. Period 1 and 2 will be separated by a wash-out phase of at least 7 days between last treatment administration in Period 1 and first treatment administration in Period 2

